2. LIST OF ABBREVIATIONS

| Term | Definition / description |
|-----------------------|---|
| 6MWT | Six-minute walking test |
| 6MWTD | Six-minute walking test distance |
| ACE | Angiotensin converting enzyme |
| AE | Adverse Event |
| AESI | Adverse Event of Special Interest |
| ALT | Alanine transaminase |
| ANCOVA | Analysis of covariance |
| ARB | Angiotensin Receptor Blocker |
| ARNI | Angiotensin Receptor-Nepilysin Inhibitor |
| ASA | acetylsalicylic acid |
| AST | Aspartate transaminase |
| ATC | Anatomical-Therapeutic-Chemical classification |
| AUC | Area Under the receiver operating characteristic Curve |
| BI | Boehringer Ingelheim |
| BIcMQ | Boehringer Ingelheim customised MedDRA Query |
| BMI | Body Mass Index |
| BP | Blood Pressure |
| bpm | beats per minute |
| BRPM | Blinded Report Planning Meeting |
| CEC | Clinical event committee |
| CHF | Chronic Heart Failure |
| CHQ | Chronic Heart Failure Questionnaire |
| CHQ-SAS | Chronic Heart Failure Questionnaire - Self-Administered Standardised format |
| CKD | Chronic Kidney Disease |
| CKD-EPI _{cr} | Chronic Kidney Disease Epidemiology Collaboration Equation |
| CML | Local Clinical Monitor |
| CTP | Clinical Trial Protocol |
| CTR | Clinical Trial Report |

| Term | Definition / description |
|----------|---|
| CRA | Clinical Research Associate |
| CRT | Cardiac Resynchronisation Therapy |
| CV | Cardiovascular |
| DBL | Database lock |
| DBP | Diastolic Blood Pressure |
| DKA | Diabetic ketoacidosis |
| DM | Diabetes Mellitus |
| DM&SM | Boehringer Ingelheim Data Management And Statistics Manual |
| ECDF | Empirical cumulative distribution functions |
| ECG | Electrocardiogramm |
| eCRF | Electronic Case Report Form |
| EF | Ejection Fraction |
| eGFR | Estimated Glomerular Filtration Rate |
| EMA | European Medicines Agency |
| EoT | End-of-Text |
| gCV | Geometric coefficient of variation |
| HF | Heart Failure |
| HFpEF | Heart Failure with preserved Ejection Fraction |
| HHF | Hospitalisation for Heart Failure |
| HLT | High-Level Term |
| IC | Informed Consent |
| ICD | Implantable Cardioverter Defibrillator |
| ICH | International Conference On Harmonisation |
| iPD | Important Protocol Deviation |
| JVD | Jugular Venous Distension |
| KCCQ | Kansas City Cardiomyopathy Questionnaire |
| KCCQ-CSS | Kansas City Cardiomyopathy Questionnaire – Clinical Summary Score |
| KCCQ-TSS | Kansas City Cardiomyopathy Questionnaire - Total Symptom Score |
| LLT | Lowest Level Term |
| LVEF | Left Ventricular Ejection Fraction |
| MedDRA | Medical Dictionary For Regulatory Activities |

| Term | Definition / description |
|-----------|--|
| MMRM | mixed model repeated measure analysis |
| MRA | Mineralocorticoid receptor antagonist |
| NT-proBNP | N-Terminal Pro-Brain Natriuretic Peptide |
| NYHA | New York Heart Association |
| OC-AD | Observed Case including data After Discontinuation |
| OC-OT | Observed Case On Treatment |
| PD | Protocol Deviation |
| PDMAP | Project Data Management and Analysis Plan |
| PGI-C | Patient Global Impression of Change |
| PGI-S | Patient Global Impression of Severity |
| PRO | Patient Reported Outcome |
| PT | Preferred Term |
| pt-yrs | patient years |
| Q1 | Lower Quartile |
| Q3 | Upper Quartile |
| ROC | Receiver Operating Characteristic |
| RS | Randomised Set |
| SAE | Serious Adverse Events |
| SBP | Systolic Blood Pressure |
| SCR | Screened Set |
| SD | Standard Deviation |
| SE | Standard Error |
| SEM | Standard Error of Measurement |
| SensRS | Sensitivity analysis set |
| SMQ | Standardised MedDRA Query |
| SOC | System Organ Class |
| T1DM | Type 1 Diabetes Mellitus |
| TBILI | Total Bilirubin |
| TS | Treated Set |
| TSAP | Trial Statistical Analysis Plan |
| ULN | Upper Limit of Normal |

| Term | Definition / description |
|--------|---|
| UTI | Urinary Tract Infections |
| WCI | Worst Case Imputation |
| WHO DD | World Health Organization Drug Dictionary |
| Y/N | Yes/No |

3. INTRODUCTION

As per ICH E9 (1), the purpose of this document is to provide a more technical and detailed elaboration of the principal features of the analysis described in the protocol, and to include detailed procedures for executing the statistical analysis of the primary and secondary variables and other data.

This TSAP assumes familiarity with the Clinical Trial Protocol (CTP), including Protocol Amendments. In particular, the TSAP is based on the planned analysis specification as written in CTP Section 7 “Statistical Methods and Determination of Sample Size”. Therefore, TSAP readers may consult the CTP for more background information on the study, e.g., on study objectives, study design and population, treatments, definition of measurements and variables, planning of sample size, randomisation.”

SAS® Version 9.4 will be used for all analyses.

4. CHANGES IN THE PLANNED ANALYSIS OF THE STUDY

4.1 CHANGES NEWLY INTRODUCED FROM THE CLINICAL TRIAL PROTOCOL

Analyses of the following endpoints have been added:

- Systolic blood pressure
- Diastolic blood pressure
- Body weight

5. ENDPOINTS

5.1 PRIMARY ENDPOINT

The primary endpoint is defined in CTP Section 2.1.2.

5.2 SECONDARY ENDPOINTS

5.2.1 Key secondary endpoints

The key secondary endpoint is defined in CTP Section 2.1.3. The scoring algorithm for KCCQ-TSS and CHQ-SAS dyspnea can be found in [Appendix 9.4](#).

5.2.2 Secondary endpoints

Secondary endpoints are listed in CTP Section 2.1.3. The scoring algorithm for the clinical congestion score can be found in [Appendix 9.5](#).

5.3 FURTHER ENDPOINTS

Further endpoints are listed in CTP Section 2.2.2.

Response in KCCQ domains at week 12: Response will be defined as an improvement of at least 5 points.

Response in CHQ domains at week 12: Response will be defined as an improvement of at least 0.5 points. Scoring algorithm for all KCCQ domains and CHQ-SAS domains can be found in [Appendix 9.4](#).

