[2668](#)], [[R17-2969](#)] in adult heart failure patients and specifically evaluates longitudinal change over time. The subscales of the CHQ-SAS are: dyspnea, fatigue and emotional function. Items are rated on a 7-point Likert scale ranging from 1 (e.g. extremely short of breath) to 7 (e.g. not at all short of breath) [[R17-2969](#)].

Control group:

Due to its mode of action empagliflozin has the potential be efficacious in treating patients with HF and could provide additional efficacy in combination with any given background therapy. However, the effect of empagliflozin in patients with heart failure has not yet been systematically assessed in a randomised clinical trial. Currently, two large clinical outcome trials are ongoing in patients with HFpEF (EMPEROR-preserved) or HFrEF (EMPEROR-reduced) to evaluate empagliflozin for the reduction of cardiovascular death and heart failure hospitalization.

The placebo-controlled design is considered ethically acceptable on the basis of appropriate criteria for patient selection and discontinuation, the ability to change background therapy to maintain, or obtain, sufficient level of hemodynamic and glyceimic control as defined in relevant local and regional guidelines for optimised standard of care.

Patients should be receiving appropriate care as defined by their physician or practitioner for all cardiovascular conditions according to the prevailing guidelines. This includes, but is not limited to, (if indicated and not contraindicated) acetylsalicylic acid, statins, a diuretic, an inhibitor of the renin-angiotensin system, a beta-blocker and a mineralocorticoid receptor antagonist, each to be given at clinically appropriate doses, and the use of implantable devices like pacemakers or implantable cardioverter defibrillators (ICDs). This should be conducted in the context of local or regional guidelines for primary or secondary CV disease prevention.

Duration:

Due to the potential early effect of empagliflozin (see above for mode of action and EMPA-REG-OUTCOME results) empagliflozin is expected to exert its effect within the early weeks of administration and therefore the peak effect on improving exercise ability is expected to be seen as early as approximately 4-8 weeks from baseline. Thus, a 12 week time point is considered suitable for the assessment of the primary endpoint.

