10.3 PATIENT REPORTED OUTCOME

10.3.1 KCCQ (Kansas City Cardiomyopathy Questionnaire)

THE KANSAS CITY CARDIOMYOPATHY QUESTIONNAIRE:

The following questions refer to your **heart failure** and how it may affect your life. Please read and complete the following questions. There are no right or wrong answers. Please mark the answer that best applies to you.

1. **Heart failure** affects different people in different ways. Some feel shortness of breath while others feel fatigue. Please indicate how much you are limited by **heart failure** (shortness of breath or fatigue) in your ability to do the following activities over the past 2 weeks.

Place an X in one box on each line

Activity	Extremely Limited	Quite a bit Limited	Moderately Limited	Slightly Limited	Not at all Limited	Limited for other reasons or did not do the activity
Dressing yourself						
Showering/Bathing						
Walking 1 block on level ground						
Doing yardwork, housework or carrying groceries						
Climbing a flight of stairs without stopping						
Hurrying or jogging (as if to catch a bus)						

2. Compared with 2 weeks ago, have your symptoms of **heart failure** (shortness of breath, fatigue or ankle swelling) changed? My symptoms of **heart failure** have become . . .

Much worse Slightly worse Not changed Slightly better Much better I've had no symptoms over the last 2 weeks

3. Over the past 2 weeks, how many times did you have **swelling** in your feet, ankles or legs when you woke up in the morning?

Every morning 3 or more times a week, but not every day 1-2 times a week Less than once a week Never over the past 2 weeks

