7.6.3 Continuous endpoints

Further continuous endpoints are generally analysed in a mixed model with repeated measures (MMRM), including visit-by-treatment interaction and baseline-by-visit interaction. An unstructured covariance structure will be used to model the within-patient errors. The MMRM analyses will also be shown graphically.

Descriptive statistics will be calculated for the value at visit and change from baseline.

- Change from baseline in KCCQ overall summary score, CSS, and individual domains at Week 6 and week 12
- Change from baseline in CHQ individual domains at week 6 and week 12
- Change from baseline in SBP at Week 6 and week 12
- Change from baseline in DBP at Week 6 and week 12

The following endpoint is assessed as part of the main analysis or sensitivity analysis of the corresponding secondary endpoint:

- Change from baseline in KCCQ TSS at Week 6
- Change from baseline in CHQ-SAS dyspnea at Week 6
- Change from baseline in Clinical Congestion Score at week 6.
- Change from baseline in NT-proBNP at week 6.

Since bodyweight is only measured at baseline and week 12, an ANCOVA model will be presented including baseline weight as a covariate.

Descriptive statistics are planned for:

- Change from baseline to week 6 and week 12 in patient-rated assessment of dyspnea and fatigue by the Borg scale as part of the 6MWT

For the following parameters measured at the follow-up visit, additionally descriptive statistics at baseline, last value on treatment and follow-up will be presented for patients with valid measurements at all three timepoints. .

- SBP
- DBP

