9.4 DERIVATION OF KCCQ AND CHQ-SAS DOMAINS

The following algorithm will be used to score the KCCQ-TSS and the CHQ-SAS Dyspnea.

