9.4.1 Kansas City Cardiomyopathy Questionnaire (KCCQ)

There are 10 summary scores within the KCCQ, which are calculated as follows:

1. Physical Limitation

Code responses to each of Questions 1a-f as follows:

- Extremely limited = 1

- Quite a bit limited = 2
- Moderately limited = 3
- Slightly limited = 4
- Not at all limited = 5
- Limited for other reasons or did not do = <missing value>

If at least three of Questions 1a-f are not missing, then the Physical Limitation Score is calculated as follows:

$$\text{Physical Limitation Score} = 100 * [(\text{mean of Questions 1a-f actually answered}) - 1] / 4$$

2. Symptom Stability

Code the response to Question 2 as follows:

- Much worse = 1
- Slightly worse = 2
- Not changed = 3
- Slightly better = 4
- Much better = 5
- I've had no symptoms over the last 2 weeks = 3

If Question 2 is not missing, then the Symptom Stability Score is calculated as follows:

$$\text{Symptom Stability Score} = 100 * [(Question 2) - 1] / 4$$

3. Symptom Frequency

Code responses to Questions 3, 5, 7 and 9 as follows:

Question 3

- Every morning = 1
- 3 or more times a week but not every day = 2
- 1-2 times a week = 3
- Less than once a week = 4

- Never over the past 2 weeks = 5

Questions 5 and 7

- All of the time = 1
- Several times a day = 2
- At least once a day = 3
- 3 or more times a week but not every day = 4
- 1-2 times a week = 5
- Less than once a week = 6
- Never over the past 2 weeks = 7

Question 9

- Every night = 1
- 3 or more times a week but not every day = 2
- 1-2 times a week = 3
- Less than once a week = 4
- Never over the past 2 weeks = 5

If at least two of Questions 3, 5, 7 and 9 are not missing, then the Symptom Frequency Score is calculated as follows:

$$S3 = [(Question\ 3) - 1]/4$$

$$S5 = [(Question\ 5) - 1]/6$$

$$S7 = [(Question\ 7) - 1]/6$$

$$S9 = [(Question\ 9) - 1]/4$$

$$\text{Symptom Frequency Score} = 100 * (\text{mean of } S3, S5, S7 \text{ and } S9)$$

4. Symptom Burden

Code responses to each of Questions 4, 6 and 8 as follows:

- Extremely bothersome = 1

- Quite a bit bothersome = 2
- Moderately bothersome = 3
- Slightly bothersome = 4
- Not at all bothersome = 5
- I've had no swelling/fatigue/shortness of breath = 5

If at least one of Questions 4, 6 and 8 is not missing, then the Symptom Burden Score is defined as follows:

$$\text{Symptom Burden Score} = 100 * [(\text{mean of Questions 4, 6 and 8 actually answered}) - 1] / 4$$

5. Total Symptom Score

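### The 5-point KCCQ response rule, read with SAP 9.4, reaches Symptom Stability, an item that already rates change over 2 weeks, so that row of the exploratory domain responder analysis does not measure response

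*SAP*

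**What the plan says.** SAP 5.3 defines response once for the whole questionnaire: "Response in KCCQ domains at week 12: Response will be defined as an improvement of at least 5 points". It then refers the reader on: "Scoring algorithm for all KCCQ domains and CHQ-SAS domains can be found in" Appendix 9.4. That appendix is headed "DERIVATION OF KCCQ AND CHQ-SAS DOMAINS", and SAP 9.4.1 opens with "There are 10 summary scores within the KCCQ, which are calculated as follows". The second of these scores is Symptom Stability, derived from Question 2 alone.

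The item text is in Protocol 10.3.1. Question 2 begins "Compared with 2 weeks ago, have your symptoms of" heart failure and asks whether they have changed. The answers run from much worse to much better, with a sixth option for patients without symptoms. SAP 9.4.1 codes 'Not changed' as 3 and codes the sixth option the same way: "I've had no symptoms over the last 2 weeks = 3".

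Two analyses use the domain scores:

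- SAP 7.6.1 compares response in KCCQ domains at week 12 by an exploratory chi-square test and shows a forest plot by domain.
- SAP 7.6.3 applies an MMRM with visit-by-treatment and baseline-by-visit terms to "Change from baseline in KCCQ overall summary score, CSS, and individual domains at Week 6 and week 12".

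Neither section exempts Symptom Stability or gives it a rule of its own.

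**The concern.** The other KCCQ domain scores describe how the patient is, or has been over the past 2 weeks, so a gain from baseline to week 12 has a plain meaning. Question 2 asks for a comparison with 2 weeks earlier. Its week-12 score describes the trend over roughly weeks 10 to 12, and its baseline score the trend over the 2 weeks before randomisation. A rule based on the difference between them asks whether the recent trend is more favourable than the trend at entry. It does not ask whether the patient is better than at entry.

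A stable, lasting benefit is then easily scored as no response, and slower deterioration can be scored as a response. The forest plot would show this row beside valid state scores with nothing to mark the difference, so a reader could take it as evidence that symptoms did not respond.

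The plan already treats its other change ratings differently. PGI-C and the Clinician Global Impression of Change are not collected at baseline (Protocol Flow Chart). They are analysed by the category chosen at the visit (SAP 7.5.2 and 7.6.2).

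**Working it through.** The plan gives no figure of its own to reproduce here. The check applies the SAP scoring and the SAP rule to every possible pair of answers.

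**Inputs**

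- Codes for Question 2 (SAP 9.4.1): much worse 1, slightly worse 2, not changed 3, slightly better 4, much better 5, no symptoms 3.
- Score (SAP 9.4.1): 100 × (Question 2 − 1) / 4.
- Rule (SAP 5.3): responder if week-12 score − baseline score ≥ 5.

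**Step 1, scores.** 100 × (1 − 1)/4 = 0; 100 × (2 − 1)/4 = 25; 100 × (3 − 1)/4 = 50; 100 × (4 − 1)/4 = 75; 100 × (5 − 1)/4 = 100. 'No symptoms' is coded 3 and also scores 50. The smallest non-zero difference is 25, so a 5-point threshold means one full answer category.

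**Step 2, change for every pair** (R = responder)

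| Baseline answer | Much worse (0) | Slightly worse (25) | Not changed (50) | Slightly better (75) | Much better (100) | No symptoms (50) |
|---|---|---|---|---|---|---|
| Much worse (0) | 0 | +25 R | +50 R | +75 R | +100 R | +50 R |
| Slightly worse (25) | −25 | 0 | +25 R | +50 R | +75 R | +25 R |
| Not changed (50) | −50 | −25 | 0 | +25 R | +50 R | 0 |
| Slightly better (75) | −75 | −50 | −25 | 0 | +25 R | −25 |
| Much better (100) | −100 | −75 | −50 | −25 | 0 | −50 |
| No symptoms (50) | −50 | −25 | 0 | +25 R | +50 R | 0 |

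Responder pairs: 5 + 4 + 2 + 1 + 0 + 2 = 14 of 36. These are counts of answer pairs, not of patients.

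**Step 3, what the pairs mean**

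- Baseline 'Not changed'; the patient improves, settles before week 10, and answers 'Not changed' at week 12: 50 − 50 = 0, non-responder, however large the improvement.
- Baseline 'Not changed', symptom-free at week 12: 50 − 50 = 0, non-responder.
- Baseline 'Slightly better', symptom-free at week 12: 50 − 75 = −25, scored as deterioration.
- Baseline 'Much better': 100 is the ceiling, so no week-12 answer gives a response.
- Baseline 'Much worse', 'Slightly worse' at week 12: 25 − 0 = +25, responder, although the patient reports that symptoms are still getting worse.
- Baseline 'Slightly worse' or 'Much worse', week-12 score 50: +25 or +50, responder.

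A week-12 score of 50 is therefore a non-response for 4 of the 6 baseline answers (not changed, slightly better, much better, no symptoms) and a response for the other 2.

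**Step 4, reach.** SAP 9.4.1 builds the Total Symptom Score from Symptom Frequency and Symptom Burden only. The Clinical Summary Score adds Physical Limitation to it, and the Overall Summary Score adds Physical Limitation, Quality of Life and Social Limitation. Question 2 enters none of them.

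**Step 5, the MMRM.** Write the change at a visit as visit score minus baseline. With a baseline-by-visit term in the model (SAP 7.6.3), subtracting baseline lowers the baseline slope at each visit by exactly 1 and leaves the treatment contrast and the residuals as they are. The treatment difference is the same whether the outcome is the visit score or its change. Only the label and the displayed mean changes are affected.

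**The case against.** **Inclusion is inferred.** The SAP never lists the domains in the forest plot. The ten scores in SAP 9.4.1 include composites that SAP 7.6.3 names apart from the individual domains, so the appendix is not purely a list of domains. This is fair, but three of the ten are composites (Total Symptom, Overall Summary, Clinical Summary). Symptom Stability is one of the seven scored directly from items, and nothing excludes it. Inclusion is the natural reading.

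**The baseline condition matters.** A reader might infer that every patient with lasting improvement, or free of symptoms, is a non-responder. The table shows otherwise: those who answered 'worse' at baseline and score 50 at week 12 are responders. A reader might also take the entry requirement of clinical stability (Protocol 3.3.2, criterion 10) to mean that most patients answer 'Not changed' at baseline. That criterion is an investigator's judgement about decompensation, and neither document gives a distribution of answers.

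**Timing.** It is tempting to cite Protocol 3.2, where "the peak effect on improving exercise ability is expected to be seen as early as approximately 4-8 weeks from baseline", as proof that symptom benefit will be over by week 10. The sentence concerns exercise ability, and it does not say when symptoms stop improving. It makes an early, settled benefit plausible and no more.

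**The MMRM.** A reader might infer that the MMRM is invalid too, or cannot show an early effect. The documents do not support this. Baseline is in the model by visit, so the contrast equals that for the visit score, and week 6 is analysed as well as week 12.

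**Small consequence.** These are further endpoints with an exploratory test. Symptom Frequency, Symptom Burden, TSS and PGI-C all capture lasting benefit. This stands and limits the weight of the point. It does not make the responder row valid.

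**Conclusion.** The responder-rule error holds. Applied as written, the 5-point rule on Symptom Stability classes lasting improvement and freedom from symptoms as non-response whenever the week-12 score is 50 and the baseline score is 50 or more. It also classes a move from 'much worse' to 'slightly worse' as response. That row of the domain chi-square tests and forest plot is not a valid measure of response.

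The conclusion rests on two things: the item wording and coding, which are explicit, and the reading that the KCCQ domains include Symptom Stability, which is natural but not spelled out. The number of patients affected, and whether the arms would differ in it, cannot be computed from the documents. A claim that the row would show a reversed treatment effect would go beyond them.

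The reach is one row of an exploratory analysis. The primary endpoint, KCCQ-TSS, and the Clinical and Overall Summary scores do not change. The MMRM needs relabelling only. The correction is still worth making, because it is cheap and the row invites misreading.

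**What to change.** 1. In SAP 5.3 and 7.6.1, name the KCCQ domains to which the 5-point rule applies, and leave Symptom Stability out of the responder test and its forest plot.
2. Add a table of Question 2 answers by arm at weeks 6 and 12, with the count of 'no symptoms' shown on its own line.
3. If a test is wanted, compare the answer at the visit with the CMH test on modified ridit scores that SAP 7.5.2 plans for PGI-C. State beforehand where 'no symptoms' is placed in the order; keeping the present code leaves the scoring algorithm intact, and the separate count makes the tie with 'Not changed' visible.
4. In SAP 7.6.3, keep the MMRM contrast if wanted, but report adjusted mean visit scores, described as a rating of the last 2 weeks and not as change from baseline.
5. Record the departure in SAP 4.1, since Protocol 2.2.2 lists response and change from baseline for the KCCQ domains without exception.

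The data are already collected. The cost is one domain fewer in an exploratory forest plot, one new table, and a small stated change from the planned analysis.

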5.4 OTHER VARIABLES

5.4.1 Demographic and other baseline characteristics

Blood pressure: Baseline SBP and DBP are taken from the vital signs assessment. If no vital signs assessment is available, the value before the start of the 6MWT will be used.

Region will be defined according to [Table 9.1:1](#)

Heart rate will display values entered in the electronic case report form (eCRF) as ‘pulse’.

